**How often do you get hypoglycemic attacks (blood glucose less than 3.6 mmol/l)?**

1. Less than once every 3 months.
2. Monthly.
3. Weekly
4. Twice to 3 times per week.
5. Daily.

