as dietitian support may be sought if the research nurse and/or PI find this to be necessary. In cases of newly diagnosed (or suspected) clinical conditions, referrals to an appropriate specialty will be made after review by the PI. If social circumstances are found to be inappropriate, for example in the case of older individuals not managing on their own, the physician in charge of the patient will be informed and steps will be taken to provide support according to the need of each individual.

In summary, the research nurse will concentrate on establishing the cause of the severe hypoglycemic episode and together with the PI will alter treatment, involve other diabetes/non-diabetes disciplines as appropriate and introduce changes to social support as required.

The research nurse will contact the patient weekly for the first month, every two weeks for the following month followed by contact at months 3, 6 and 12. Face to face contact with the patient will be arranged at enrolment, 1, 3 and 12 months. Patient will be asked to fill in the questionnaire at enrolment and end of 3rd month, with selected patients asked to complete the form again at 12 months (explained in Figure 4). Blood tests will be arranged as detailed above. In the standard arm, patient will be contacted only once as per current arrangement and subsequent treatment left to the discretion of the attending physician (summarised in Figure 4).

**Figure 4.** Summary of the preliminary interventional part of the study. U&Es: urea and electrolytes, LFTs: liver function tests, UACR: urinary albumin/creatinine ratio, MACE: major adverse cardiovascular events, m:

month, d: day. Questionnaire will be done at enrolment and 3 months in both groups. If a significant difference exists between the two time points in the same patient, the questionnaire will be repeated at 12 months. Clinical outcome at 12 months will also include frequency of hypoglycemia, analysed separately.

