**How often do you test your blood glucose (sugar) levels?**

1. At least twice a day with additional testing as needed.
2. At least once a day.
3. Less than once a day but at least twice a week.
4. Less than once a week.
5. Never.

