**In the past 12 months, how many times have you had hypoglycemic attacks requiring the assistance of another person?**

1. None.
2. Once.
3. On 2-3 occasions.
4. On 4-5 occasions

5. More than 5 times.

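### The severe-attack question still looks back 12 months at the 3-month visit, so three quarters of its window precedes randomisation

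*Combined protocol and SAP*

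**What the plan says.** Appendix 1 is the patient questionnaire. Three of its items matter here.

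- **Severe attacks.** The item asks "In the past 12 months, how many times have you had hypoglycemic attacks requiring the assistance of another person". The answers run none, once, two or three, four or five, more than five. These categories are complete.
- **Attack frequency (glucose below 3.6 mmol/l).** The answers are "Less than once every 3 months", then monthly, weekly, "Twice to 3 times per week" and daily. The item states no recall period.
- **Glucose testing.** The third answer is "Less than once a day but at least twice a week" and the fourth is "Less than once a week".

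The timing is in the Interventional study section, in the Figure 4 caption: "Questionnaire will be done at enrolment and 3 months in both groups". A later form is conditional: "If a significant difference exists between the two time points in the same patient, the questionnaire will be repeated at 12 months". No part of the protocol gives the 3-month form a different look-back, or says how to score an answer that fits none of the options.

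On outcomes, the Aims list future hypoglycemic events first. The Statistical analysis section bases the sample size on mortality. The Figure 4 caption adds hypoglycemia frequency as a separate 12-month outcome but names no data source for it.

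**The concern.** A question meant to show what happened after randomisation should cover mainly the time after randomisation. Used at 3 months, the severe-attack item covers mostly the time before. Both arms share that earlier period, and everyone entered because of an attack attended by the emergency services, so most of what the item records at 3 months cannot have been altered by the nurse support.

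Two things are at stake. The first is the between-arm comparison on this item at 3 months. The second is the 12-month repeat, which depends on a change between a patient's enrolment and 3-month answers. An item built to change little will seldom contribute to triggering it.

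The gaps in the other two scales are a smaller matter of the same kind: some patients have no option that fits and must choose a neighbour.

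**Working it through.** The plan states no figure to reproduce; the check sets the recall window against the visit schedule.

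**Inputs.** From the protocol: look-back 12 months; forms at enrolment and 3 months in both arms; entry after an emergency-service-attended attack; 200 patients per arm; Mann-Whitney for non-normal data. Assumed, because the protocol gives no rates: randomisation at enrolment; enrolment within nine months of the qualifying attack; accurate recall; a constant rate of L other severe attacks a year; a rate ratio RR after randomisation in the intensive arm.

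**1. Share of the window before randomisation.** (12 − 3)/12 = 9/12 = 75%.

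**2. Apparent effect, qualifying attack left out.** Ratio = (9 + 3·RR)/12.
- RR = 0.5: (9 + 1.5)/12 = 0.875, so a 50% reduction appears as 12.5%.
- RR = 0.7: (9 + 2.1)/12 = 0.925, so a 30% reduction appears as 7.5%.

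**3. Apparent effect, qualifying attack counted.** Ratio = (1 + 0.75·L + 0.25·L·RR)/(1 + L). With RR = 0.5:

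| L per year | Calculation | Ratio | Apparent reduction |
|---|---|---|---|
| 0.5 | 1.4375/1.5 | 0.958 | 4.2% |
| 1 | 1.875/2 | 0.938 | 6.3% |
| 2 | 2.75/3 | 0.917 | 8.3% |
| 4 | 4.5/5 | 0.900 | 10.0% |

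**4. What this does to a test.** Simulation on the item's own five categories: 200 per arm, Mann-Whitney, two-sided 0.05, RR = 0.5, gamma-Poisson counts with shape 1, 1,500 runs per setting.

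| L per year | Power, 12-month window with qualifying attack | Power, 3 months from randomisation |
|---|---|---|
| 1 | 13% | 71% |
| 2 | 16% | 90% |
| 4 | 17% | 97% |

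**5. Within-patient change.** The enrolment and 3-month windows share nine months. Take a patient with four other attacks a year, evenly spaced, whose severe attacks stop completely at enrolment. At enrolment the count is 1 + 4 = 5; at 3 months it is 1 + 3 = 4. Both fall in the four-or-five category, so the item shows no change. On a 3-month window without the qualifying attack, the same patient goes from one to none.

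**6. Scale gaps.** The frequency item has no option for once every three months up to just under monthly, for two or three a month, for four to six a week, or for more than daily. The testing item has none for once up to just under twice a week. An illustration for the frequency item assumed log-normal rates (median 2 to 4 a month, log-SD 1.2), a true 30% reduction, and gap respondents choosing either neighbour at random. Power was about 73% to 75% with the gaps and 77% to 79% with contiguous bands, a loss of about four percentage points.

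**The case against.** The best defence is that the questionnaire does not carry the trial's main result. The sample size rests on mortality, the Plan of investigation describes a separate ambulance reporting pathway, and nothing makes this item the measure of future hypoglycemic events. That stands, and it limits the scope. A reader might infer that any effect of the intervention is diluted; the protocol does not support that. The point concerns effects measured on this item at 3 months.

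It can also be said that a 12-month window is sensible at enrolment, as history, and at 12 months, where it matches follow-up. That is right; only its use at 3 months is at fault.

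A more technical defence is that pre-randomisation attacks cancel in expectation, so the absolute difference in mean counts stays 0.25·L·(1 − RR). This is true of raw counts. But the nine earlier months add variance, and the item records categories that widen as counts rise. The planned between-group tests are unadjusted, so the enrolment answer is not used to remove that variance. The power figures above show the cost.

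On the gaps, three stronger readings are tempting, and none is supported:

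- *That a large share of patients, say 37% to 59%, has no valid frequency answer.* That range comes from imposing a 3-month count and a Poisson mean of 0.5 to 3. The item asks for a usual rate, and the protocol gives no rates. The result follows the mean chosen: the chance of exactly one or two attacks is e^−1.5 × (1.5 + 1.125) = 59% at a mean of 1.5, but e^−6 × (6 + 18) = 6% at a mean of 6.
- *That the gaps bias towards no effect.* Patients know their arm and may resolve a gap differently by arm, so the direction is not established.
- *That the testing gap lies where the intervention acts.* The Interventional study section encourages two or more tests a day, which the first option captures. The gap is near once a week.

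**Conclusion.** The mismatch is real and follows from the text: at 3 months, 75% of the severe-attack window precedes randomisation, and *none* is normally not an accurate answer. A true halving appears as 12.5% at a constant rate, and as about 4% to 10% with the qualifying attack counted and 0.5 to 4 other attacks a year. The 75% needs only that randomisation takes place at enrolment. The apparent reductions rest on the constant rate and, where used, on L; the power figures also rest on the assumed distribution and 200 respondents per arm.

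The consequence is a weak 3-month comparison on this item, and an item less likely to prompt the 12-month form. Mortality and ambulance-reported events are not affected. Whether the 12-month hypoglycemia outcome is affected cannot be said, because its source is not stated. The gaps in the other two scales are a minor wording matter, worth correcting at the same time.

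**What to change.** **Severe-attack item.** Keep the five answer categories and change the window by form:
- Enrolment: attacks in the past 3 months, excluding the qualifying attack; keep the 12-month question as a separate history item.
- 3 months: attacks in the past 3 months, or since enrolment.
- 12 months: keep the 12-month window.

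**Minor edits at the same time.**
- Frequency item: state a recall window and use contiguous, exhaustive bands, for example *none in the past 3 months; up to once a month; more than monthly up to weekly; more than weekly but less than daily; daily or more*.
- Testing item, fourth option: *less than twice a week, but sometimes*. This closes the gap and separates it from *never*.

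The cost is rewording three items before first use and one extra history question at enrolment. Answers already collected on the 12-month window could not be converted to a 3-month count afterwards.

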**In the past 12 months, how many times have you had hypoglycemic attacks requiring the assistance of another person?**

1. None.
2. Once.
3. On 2-3 occasions.
4. On 4-5 occasions

5. More than 5 times.

**Do you get hypoglycemic warning with low glucose levels?**

1. Always.
2. Yes but they are getting less prominent.
3. Sometimes I do not.
4. Rarely and very little.
5. Not at all.

**Do you know why diabetes control is important?**

1. Yes, I fully understand.
2. I think I know.
3. I have a rough idea.
4. I may but not that sure.
5. I have no idea.

**Do your hypoglycemic episodes have a major impact on your quality of life?**

1. Never.
2. Rarely.
3. Sometimes.
4. They have a major impact on quality of life.
5. Hypoglycemia is making me miserable.

**Is close support from a diabetes nurse helpful to control your blood glucose?**

1. Definitely, no question about it.
2. Yes, but it depends on the person.
3. To some extent.
4. Only marginal benefit.
5. Useless.

**For insulin users: Do you know how to adjust/modify your insulin doses according to your glucose readings?**

1. I am in full control.
2. Yes, but I may need occasional advice.
3. Yes, but prefer to have advice for reassurance.
4. I have little knowledge.
5. I have no idea.

**Do you know what to do when you get severe hypoglycemia?**

1. Yes.
2. I have a good idea.
3. I know some but not all aspects.
4. My knowledge is weak.
5. I have no idea.

**Does close diabetes nurse support make you more confident at managing your diabetes?**

1. Definitely.
2. Certainly has an effect to some extent.
3. Has a marginal effect.
4. Very little effect.

5. No effect at all.

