### **Aims**

The proposed work is divided into two parts through an observational and an interventional study.

1. Observational study: characterise individuals with severe hypoglycemia.
2. Interventional preliminary study: investigate the effect of regular glucose monitoring and specialist nurse input into a) future hypoglycemic events, b) confidence with diabetes management/quality of life and c) clinical outcome.

[figure not shown]

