### Observational study

Various details will be collected to elucidate the characteristics of patients undergoing severe hypoglycemia requiring emergency services intervention.

**Demographic and general data.** Address, age, sex, type of diabetes and duration, weight, body mass index, blood pressure, presence of macrovascular and microvascular complications, current treatment, status at home (living alone), driving status, alcohol consumption, smoking history, mobility, non-diabetes related co-morbidities. We will also clarify who made the ambulance call (patient/carer/other).

**Patient questionnaire (see appendix 1).** This will address whether a patient feels confident regarding managing his/her diabetes, how often glucose is monitored, can the patient adjust insulin, does the patient understand the dangers of hypoglycemia, presence of hypoglycemia awareness, frequency of low glucose levels, treatment options of hypoglycemia.

**Examination.** Check injection sites for lipoatrophy or lipohypertrophy and examine for signs of peripheral neuropathy (monofilament test).

**Blood and urine tests.** These will be arranged as part of routine clinical care in both groups, unless recent blood tests have been done. The following tests will be included: HbA1c, urea and electrolytes, liver function tests, full lipid profile, thyroid function tests (where appropriate), urinary albumin/creatinine ratio (ACR). HbA1c will be measured every 3 months, U&Es, LFTs and lipid profile 6 monthly. ACR will be checked at enrolment and at 12 months. All above tests will be requested more frequently if clinically indicated.

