### **Interventional study**

We will conduct a preliminary interventional study, where patients will be randomised to either intensive monitoring/treatment modification, where patients are closely followed up by the research nurse, or conventional therapy following local protocols. Individuals in the interventional part of the study will be:

[figure not shown]
- i) Regularly contacted by the research nurse as detailed below.
- ii) Encouraged to check their glucose levels as appropriate, at least twice a day or more frequently as necessary.
- iii) Special leaflets regarding different aspects of diabetes will be given to patients and will be discussed. These will include leaflets for alcohol, exercise, Carbohydrate counting and awareness as appropriate (please see below).
- iv) Patients will have a dedicated phone number that they can ring for urgent advice.
- v) There will be a dedicated email line set up to answer less urgent queries and help with patient support. An email system is already set up in Leeds by the PI, and patients using this service experienced significant improvement in diabetes control (data not shown).

The research nurse will make every attempt to establish the cause of severe hypoglycemia by taking a detailed medical history in order to clarify clinical comorbidities and assess social circumstances including alcohol intake, patient independence and help provided by carers. The nurse will also document current medications with special attention to dose and frequency of hypoglycemic agents, including insulin. Routine blood tests to assess overall glycemic control, renal and liver function will be performed, which may further help to shed light on the cause of low blood glucose. Hypoglycemic treatment may be changed in cases of concern but only after review by the PI, and the medical team in charge of the patient will be informed. For example, a sulphonylurea may be stopped or replaced if deemed inappropriate for the patient and insulin regimens/doses may also be altered. Follow up of patients after changes to medical therapy are detailed below but some may have more frequent contact with the nurse as per clinical need. The nurse employed will have extensive experience in the management of diabetes and will have the necessary knowledge to adjust doses/mixtures/intervals of insulin as appropriate, with adequate support provided by the PI in difficult clinical scenarios. Other diabetes disciplines, such

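### Appendix 1 has no direct, arm-neutral item on confidence: the one item that names it asks about the effect of the randomised nurse support

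*Combined protocol and SAP*

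**What the plan says.** The Aims section lists, among the effects of the intervention to be studied, "b) confidence with diabetes management/quality of life". The Patient questionnaire paragraph of the Observational study section says of Appendix 1: "This will address whether a patient feels confident regarding managing his/her diabetes".

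The Interventional study section randomises patients to an intensive arm, "where patients are closely followed up by the research nurse, or conventional therapy following local protocols". For the comparator it says: "In the standard arm, patient will be contacted only once as per current arrangement". The Figure 4 legend adds: "Questionnaire will be done at enrolment and 3 months in both groups". A patient whose answers differ significantly between those two times completes it again at 12 months.

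Of the 15 items in Appendix 1, two are about nurse support: "Is close support from a diabetes nurse helpful to control your blood glucose" and "Does close diabetes nurse support make you more confident at managing your diabetes". The second is the only item that names confidence. Its five options grade the size of an effect (the second reads "Certainly has an effect to some extent"), and none is provided for a patient who has had no such support.

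The Statistical analysis section gives general rules for between-group tests. It names no questionnaire item or score as the measure of confidence.

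**The concern.** The plan promises to record how confident the patient feels. The item that appears to deliver this asks instead whether a particular kind of support raises confidence. Because that support is the intervention, the answer depends on which arm the patient is in, whatever the patient's actual confidence. An analyst who follows the plan and compares this item between arms could report a difference in confidence that only reflects who had the research nurse.

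The fault could also spread. The rule for repeating the questionnaire at 12 months rests on a within-patient difference, and nothing keeps the two nurse-support items out of it. Receipt of the nurse could then influence who is measured again.

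**Working it through.** No arithmetic beyond counting applies, so the check sets the items against the aim.

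**Step 1. Sort the 15 items of Appendix 1.**

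| Type of item | Number | Items |
|---|---|---|
| Direct and arm-neutral on confidence | 0 | none |
| Dependent on nurse support | 2 | helpfulness of nurse support; its effect on confidence |
| Arm-neutral and indirectly related to confidence | 3 | worry about glucose testing; adjusting insulin; knowing what to do in severe hypoglycemia |
| Other | 10 | understanding, education, testing habits, hypoglycemia frequency and warning, reasons for control, quality of life, driving |

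The counts add up: 0 + 2 + 3 + 10 = 15.

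**Step 2. What the confidence item measures.** Its scale runs from a definite effect of nurse support (category 1) to none (category 5). It grades an attributed effect and does not record a level of confidence. Two hypothetical patients show the consequence:

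- A standard-arm patient who is very confident and has had no close nurse support may truthfully choose category 5.
- An intensive-arm patient who is still unsure, but less so since the nurse began calling, may truthfully choose category 1.

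Read as confidence, the item ranks these two the wrong way round.

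**Step 3. Comparison between arms.** Both arms answer at 3 months. By then the intensive arm has had weekly contact for a month, two-weekly contact for the next month and contact at month 3. The standard arm has had its single contact and then care at the attending physician's discretion. The same words therefore refer to different experiences, and the difference in experience is the randomised one.

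**Step 4. Change from enrolment.** At enrolment no patient in either arm has yet received the trial intervention. By 3 months the intensive arm has. The item changes meaning over time in that arm in a way it does not in the standard arm, so subtracting the enrolment answer does not remove the problem.

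**Step 5. What the three indirect items can carry.** The Patient questionnaire paragraph lists insulin adjustment and the treatment of hypoglycemia separately from feeling confident, so the plan itself treats them as other topics. The insulin item is for insulin users only. In the Leeds data in the Background, 28% of the type 2 patients were not on insulin. The testing item asks about worry. None is named as a measure for aim (b), and choosing one after seeing the data would be post hoc.

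**Step 6. The other half of aim (b).** Appendix 1 has an item on the effect of hypoglycemic episodes on quality of life. It does not mention the nurse and can be compared between arms.

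**The case against.** The strongest reply is that confidence is not lost. Both arms complete the same form, and the indirect items come close. The testing item runs from never worrying because one knows what to do, to being terrified and not knowing how to handle the readings. The insulin item runs from full control to no idea. The plan never says that the nurse-support item is the confidence endpoint. This stands in part. A reader might infer that confidence cannot be compared between arms at all, or that every piece of data on it is spoiled. The documents do not support that, because the indirect items are arm-neutral. What they lack is directness and designation.

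A reader might also infer that standard-arm patients have no nurse support, or that most patients have none at enrolment. The documents do not say so. The Figure 2 legend places a diabetes nurse specialist in the existing pathway, and the standard arm's later care is left open. The supportable statement is that the arms differ by design in close, repeated support from the research nurse, and that nobody has had it at enrolment.

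The nurse-support items also have a legitimate use. The questionnaire serves the observational study too, and patients' views of nurse support can be described there. This stands, and is a reason not to delete those items or restrict them to one arm.

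Appendix 1 says the research nurse will not see the answers. That may reduce courtesy in answering, but it does not change what the question means in each arm.

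Finally, the study is described as preliminary and its sample size rests on mortality. That limits the consequence but does not repair the measure.

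**Conclusion.** The point holds in a limited form. Appendix 1 contains no direct, arm-neutral measure of confidence, although the Observational study section describes one and aim (b) needs one. The single item of 15 that names confidence measures the perceived effect of the randomised support. Neither a between-arm difference nor a change from enrolment on it validly measures confidence. Three indirect items remain, one for insulin users only and none designated.

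The quality-of-life part of aim (b) and the mortality basis of the sample size are untouched. The conclusion rests on the wording of the items and on the designed difference between arms. It needs no assumption about how much nurse support patients receive outside the trial. It is best classed as a cheap improvement.

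**What to change.** - Add one item that asks for the level of confidence without mentioning the nurse, for example: *How confident do you feel about looking after your diabetes?* Give it five levels from very confident to not at all confident, and ask it in both arms at every questionnaire.
- Name this item in the Statistical analysis section as the confidence measure for aim (b).
- Keep the two nurse-support items for all patients as descriptive data. State that they are excluded from the between-arm comparison of confidence and from the within-patient difference that triggers the 12-month questionnaire.

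The cost is one more question on the form and a short addition to the analysis text. No extra visits or staff are needed, and the observational study loses no data.
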